7.3.2. Secondary Mechanistic Analysis

Soluble Mediators:

A total of 32 mediators in nasal samples (taken at day -21, 0, 2, 3, 4, 5, 7, 10) and bronchoscopic samples (taken at day -8, day 5) will be measured for each subject.

Values of soluble mediators obtained from bronchial samples will be presented using summary statistics per treatment group and visit. An additional table will summarise per treatment group (for each mediator) the difference in values between mediators taken at D-8 and D5. Analysis to investigate any difference in effect of OC459 and placebo for each mediator will be performed using the difference in values via unpaired (two-sample) t-test or Mann-Whitney U tests for non-parametric data.

Values of soluble mediators obtained from nasal samples will be presented using summary statistics per treatment group and visit. An additional table will summarize per treatment group (for each mediator) the difference between D-21 and peak value (the highest value measured between D0 and D10).

Taking the difference between D-21 and peak value, analysis to determine the difference in effect of OC459 and placebo for each mediator will be performed using unpaired (two-sample) t-test or Mann-Whitney U tests for non-parametric data.

Differences will be considered significant at $P < 0.05$ within a hierarchy of the primary outcome, and interpreted more cautiously for secondary efficacy outcomes, (likewise more so for exploratory outcomes). All P values are two-sided.

Leukocyte numbers:

Values of leukocyte numbers obtained from bronchial samples / flow cytometry will be presented using summary statistics per treatment group and visit. An additional table will summarise per treatment group (for each cell type) the difference in values between samples taken at D-8 and D5. Analysis to investigate any difference in effect of OC459 and placebo for each cell type will be performed using the difference in values via unpaired (two-sample) t-test or Mann-Whitney U tests for non-parametric data.

Eosinophil counts:

Values of blood and sputum eosinophilia will be presented using summary statistics per treatment group and visit. Analysis to investigate any difference in effect of OC459 and placebo for blood and sputum eosinophilia will be performed using the difference in values via unpaired (two-sample) t-test or Mann-Whitney U tests for non-parametric data.

7.3.3. Correlation testing between Secondary Outcomes

Potential causal relationships between outcome variables will be investigated using Spearman’s rank correlations. Tests will be carried out between (but not limited to) the following:

Baseline values of:
 
 • ACQ-6 (day 0) • FeNO (day 0) • Blood eosinophils (day -8) • Serum IgE (day -8) • PC₂₀ (day -9) • Skin prick test (from screening) 
 ○ # of allergens ○ Sum of wheal diameters (mm) • Soluble mediators 	vs	
Peak and AUC values of:
 
 • Lower respiratory symptom score • Upper respiratory symptom score • Virus load • Morning PEFr (peak decline) • Morning FEV₁ (peak decline) • Soluble mediators
---	----	--

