10.2 DATA ANALYSIS

Subjects completing the study protocol will be defined as infected or un-infected (neutralising antibody to RV-16 at 6 weeks post inoculation at a titre $<1:4$ and no detection of RV-16 by qPCR in nasal lavage, sputum or BAL at any point after inoculation). Only subjects with confirmed rhinovirus infection will be included in statistical analysis.

Quantitative assessments of symptom scores, lung function, exhaled nitric oxide (FeNO), airway hyperresponsiveness (histamine challenge, PC_{20}), virus load, inflammatory cell numbers and inflammatory markers will be compared within subjects to determine differences between baseline and during infection. Within-subject differences will be analyzed using ANOVA and 2-tailed paired Student's t-tests or Wilcoxon signed rank test as appropriate.

Differences between the patients taking OC459 and placebo group will be analyzed using unpaired parametric or non-parametric analysis as appropriate at each phase of the study. Correlations between (but not limited to) the following will be examined using Spearman's rank correlations to investigate possible causal relationships:

- illness severity (symptoms, lung function, airway hyperresponsiveness)
- virus load
- inflammatory cell counts
- inflammatory markers
- gene expression

Data and all appropriate documentation will be stored for a minimum of 10 years after the completion of the study, including the follow-up period.

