4.4. Sample Size

An overall population size of 44 asthmatic subjects was based on the following assumptions:

- Type I error probability $\alpha = 5\%$
- Effect size = $(\mu_1 - \mu_0) / \sigma$
 - μ_i = mean PEP in group i ($i=1$: OC459, $i=0$: placebo),
 - σ = standard deviation of PEP
- PEP is primary end-point (=total daily lower respiratory symptom scores over D0 to D14, potential maximum of 315).

Based on a previously completed trial with similar design conducted at the same study site [10], σ is estimated to be 21.15 and the effect size equal to 22.21, yielding $n=15$ evaluable subjects per treatment group at 80% power. This is grossed-up for 80% rhinovirus inoculation success and adjusted for expected drop-outs to yield 22 enrolled patients per treatment group.

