7.2. Primary Analysis

Uncorrected lower respiratory symptom scores collected from D0 to D14 will be aggregated to create an overall total for each patient. Where patient scores are missing, data will be imputed based upon rules set within Section 7.5. Patients missing $\geq 20\%$ of score data will be excluded from any additional per-protocol analyses.

Data will be presented using summary statistics per treatment group and will include median and interquartile range (IQR). A supplementary plot showing individual measurements for both groups with a box & whisker overlay showing median and IQR will be produced.

Primary analysis to test for difference between the mean aggregated scores of the two treatment groups will be carried out using Mann-Whitney U tests. Differences will be considered significant at $P < 0.05$. All P values are two-sided.

An additional secondary analysis will take place correcting the scores for bronchoscopy-related symptoms. Full methodology will be clarified within Section 7.3.1 below.

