7.4.3. Exploratory Correlation Testing

We will correlate lower respiratory symptom scores with the ACQ (which reflects symptoms over the last 7 days) at two timepoints:

- ACQ-6 at day -9 vs sum of lower respiratory symptom scores day -15 to day -9 inclusive
- ACQ-6 at day 10 vs sum of lower respiratory symptom scores day 4 to day 10 inclusive

Potential relationships between the above will be investigated using Spearman’s rank correlations.

Potential relationships between outcome variables and antiviral response variables will be investigated using Spearman’s rank correlations. Tests will be carried out between the following:

Efficacy Analysis Variable
 
 • Lower respiratory symptom score (peak and AUC) • Upper respiratory symptom score (peak and AUC) • Virus load (peak and AUC) • Morning PEFr (peak decline) • Morning FEV₁ (peak decline) • FeNO (peak increase) • Any cytokine statistically induced by infection (peak increase) 	vs	
Antiviral Response Variable:
 
 • interferon levels (β, λ1, λ2/3) • mRNA levels of interferons (β, λ1, λ2/3) • mRNA levels of a panel of interferon-stimulated genes (MxA, RIG-I, OAS, viperin, IP-10, PKC)
--	----	---

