For non-parametric data variables: See Table 2.03

Table 3.07 – Summary of Effect of Treatment on Viral Load Results

Laboratory Test (units)*	Treatment	Visit	n	Mean	SD	Median	Min.	Max.	IQR
xxxxx (xxxx)	Control								
	Treatment								

*Variables for inclusion as per section 6.3.1

Table 3.08 – Statistical Testing on Effect of Treatment Viral Load Results

For normally distributed data variables:

Source	DF	Sum of Squares	Mean Square	F Value	Pf > F
Model	XX	XX	XX	XX	XX
Error	XX	XX	XX		
Corrected Total	XX	XX			

For non-parametric data variables: See Table 2.03

Secondary Mechanistic Analysis

Table 3.09 - Summary of Nasal Soluble Mediators per visit

Laboratory Test (units)*	Treatment	Visit	n	Mean	SD	Median	Min.	Max.	IQR
xxxxx (xxxx)	Control								
	Treatment								

Table 3.10 - Summary of Change from Baseline to Peak Value for Nasal Soluble Mediators

See Table 3.09

Table 3.11 - Statistical Testing of Nasal Soluble Mediators

For normally distributed data variables:

Source	DF	Sum of Squares	Mean Square	F Value	Pf > F
Model	xx	xx	xx	xx	xx
Error	xx	xx	xx		
Corrected Total	xx	xx			

For non-parametric data variables: See Table 2.03

Table 3.12 - Summary of Bronchial Soluble Mediators per visit (D-8, D5)

See Table 3.09

Table 3.13 - Summary of Change from Baseline (D-8) to Infection (D5) for Bronchial Soluble Mediators

See Table 3.09

Table 3.14 - Statistical Testing of Bronchial Soluble Mediators

See Table 3.11

Table 3.15 - Summary of Leukocyte Numbers per visit (D-8, D5)

See Table 3.09

Table 3.16 - Summary of Change from Baseline (D-8) to Infection (D5) for Leukocyte Numbers

See Table 3.09

Table 3.17 - Statistical Testing of Leukocyte Numbers

See Table 3.11

Table 3.18 - Summary of Blood and Sputum Eosinophilia

See Table 3.09

Table 3.19 - Summary of Change from Baseline to Peak Value for Blood and Sputum Eosinophilia

See Table 3.09

Table 3.20 - Statistical Testing for Blood and Sputum Eosinophilia

[figure not shown]
See Table 3.11

Secondary Analysis – Correlation Testing

Table 3.21 - Spearmans Rank Correlation Testing

Pearson Correlation Coefficients Prob > r under H0: Rho=0 Number of Observations		
	Var 1	Var 2
Var	XXXX	XXXX
XXXXXXXX.	XXXX	XXXX
	XX	XX
Var	XXXX	XXXX
XXXXXXXX.	XXXX	XXXX
	XX	XX

Figure 3.22 - Correlation Matrix

The above matrix can contain the following:

Baseline values of:

- ACQ (day 0)
- FeNO (day 0)
- Blood eosinophils (day -8)
- Serum IgE (day -8)
- PC₂₀ (day -9)
- Skin prick test (from screening)

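### The Spearman correlations meant to look for causal links have no term for treatment arm, although most of the dated baselines are measured 12 to 21 days into randomised drug

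*SAP*

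**What the plan says.** SAP 7.3.3 says "Potential causal relationships between outcome variables will be investigated using" Spearman's rank correlations. Protocol 10.2 gives the same purpose: "rank correlations to investigate possible causal relationships". In SAP 7.3.3 one side is a list of baseline values: ACQ-6 and FeNO at day 0, blood eosinophils and serum IgE at day -8, PC20 at day -9, skin-prick results from screening, and soluble mediators with no day given. The other side is peak and AUC values of symptom scores, virus load and mediators, and peak decline in morning PEFR and FEV1.

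SAP 7.4.3 adds exploratory correlations: "Potential relationships between outcome variables and antiviral response variables will be investigated using" the same method, with interferon and interferon-stimulated-gene results on one side and symptom scores, virus load, lung function, FeNO and cytokines on the other.

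None of these sections mentions treatment arm. The output shell, "Table 3.21 - Spearmans Rank Correlation Testing", is a generic variable-by-variable grid. The schedule (SAP 4.9) has drug or placebo given daily from day -21 to day 14, and SAP 4.10 sets baseline at the last value before inoculation, day 0 where available.

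**The concern.** The stated question is whether one variable drives another. A correlation over both arms tests something else, namely association in a mixture of treated and untreated subjects. If OC459 lowers both variables, treated subjects cluster at the low end of each and placebo subjects at the high end. A positive correlation then appears even when the two are unrelated within either arm. If the within-arm relationship is negative, the same shift cancels part of it.

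The plan itself treats a drug effect before inoculation as possible. SAP 7.4.1 tests for one in cell counts and nasal mediators. SAP 7.5 declines to substitute an earlier baseline in treated subjects, virus load excepted, while allowing it in placebo subjects. On the outcome side, the day 0 to 14 lower respiratory total is the endpoint the trial is powered to move. In 7.4.3 the interferon responses are themselves compared between arms under 7.4.2, so a drug effect is contemplated on both sides there, whatever is decided about baseline days.

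At stake is how the mechanism-of-action objective is read. If the drug works, some of these correlations would restate the treatment effect and be described as causal links.

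**Working it through.** **Inputs from the documents**

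- SAP 4.4: "Type I error probability $\alpha = 5"%. SAP 7.2: "All P values are two-sided".
- SAP 4.4: "σ is estimated to be 21.15 and the effect size equal to 22.21, yielding $n=15$ evaluable subjects per treatment group at 80% power". The 22.21 is read as a raw difference, which gives d = 22.21/21.15 = 1.05 SD.
- SAP 4.4: "This is grossed-up for 80% rhinovirus inoculation success and adjusted for expected drop-outs to yield 22 enrolled patients per treatment group".
- Time on drug: day -9 is 12 days after day -21, day -8 is 13 days, day 0 is 21 days.

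**The plan's own figure.** Normal approximation: n = 2(1.96 + 0.84)²/1.05² = 14.2, so 15 per arm, with 82.0% power at 15. A two-sample t-test needs 15.26 (16), with 79.3% power at 15. The stated 15 reproduces. It is the only stated figure that sets the size of the correlation analyses; none is given for the correlations themselves.

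**Expected pooled correlation.** With 1:1 allocation, within-arm correlation r and drug shifts dx and dy in SD units:

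ρ = (r + dx·dy/4) / √[(1 + dx²/4)(1 + dy²/4)]

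- r = 0, both shifts 0.5: 0.0625/1.0625 = 0.06
- r = 0, both shifts 1.05: 0.2757/1.2757 = 0.22
- r = -0.5, both shifts 0.5: -0.4375/1.0625 = -0.41
- r = -0.5, both shifts 1.05: -0.2243/1.2757 = -0.18

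**Rejection rates by simulation.** Normal data, 15 per arm, 20,000 replicates, two-sided 5%. The pooled test is Spearman on 28 df. The adjusted test is the partial Spearman: rank over both arms, centre the ranks within arm, correlate, 27 df. The documents give no drug effect on the correlated baseline variables, so the effects are assumptions shown as a range.

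No within-arm correlation (false positives):

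| Drug effect on the two variables, SD | Pooled | Adjusted for arm |
|---|---|---|
| 1.05 and 0 | 5% | 5% |
| 0.5 and 0.5 | about 6% | 5% |
| 1.05 and 0.5 | about 9% | 5% |
| 1.05 and 0.8 | 15% | 5% |
| 1.05 and 1.05 | 22% | 5% |

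SAP 5.4 assigns ex vivo analyses to the extended set, which can exceed 30 subjects. At 22 per arm, the number enrolled and so an upper bound, the 1.05/1.05 row becomes 29.7% pooled and 4.8% adjusted.

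Within-arm r = -0.5, both variables lowered by drug (power):

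| Drug effect on both, SD | Pooled | Adjusted for arm |
|---|---|---|
| 0 | 77% | 75% |
| 0.5 | 57% | 75% |
| 1.05 | 10% | 74% |

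**Cost of adjusting.** Suppose drug shifts X by 1.05 SD and reaches Y only through X, with within-arm r = 0.5, so Y shifts by 0.5 × 1.05 = 0.525 SD. Power is 86% pooled and 75% adjusted.

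**The case against.** The documents do not say that the arms are pooled. They are silent, and pooling is an inference, though the natural one. A reader might take the lack of a treatment row in the Table 3.21 shell as proof. It is not. The shells for between-arm tests of normally distributed data (Tables 3.06, 3.08 and 3.11) also show no treatment row, so nothing follows from the layout.

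A reader might also infer that every listed baseline is on drug. The skin-prick items come from screening and cannot carry the artefact. The mediator day is not stated in 7.3.3: SAP 4.10 points to day 0, while 7.3.2 uses day -21 for nasal and day -8 for bronchial samples.

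The artefact is conditional. It needs a real drug effect on both variables. At 0.5 SD on each, false positives barely rise, although masking is already visible. The case of r = -0.5 with 1.05 SD effects is constructed to show the mechanism and is not a forecast.

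Adjustment has a price beyond one degree of freedom. If drug acts on one variable through the other, which is the kind of mechanism the trial seeks, the between-arm variation is informative and the adjusted coefficient discards it.

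Finally, mechanism is addressed mainly by the between-arm comparisons in 7.3.2 and 7.4.1, and the SAP says that secondary results will be read cautiously and exploratory ones more so. That limits the consequence. It does not remove the problem: caution concerns the strength of evidence, whereas here the pooled coefficient answers a different question from the one stated.

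All of these limits stand. None shows that an unadjusted pooled correlation can support a causal reading.

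**Conclusion.** The concern holds as a minor point. A correlation with no arm term cannot separate a treatment effect on two variables from a relationship between them, and five of the listed baselines (ACQ-6, FeNO, blood eosinophils, IgE, PC20) are measured on drug. At 15 per arm the false-positive rate runs from about 6% to 22% across the assumed effects of 0.5 to 1.05 SD on both variables, and stays at 5% if only one moves. Power to see a relationship of opposite sign can fall from about 75% to between 57% and 10%. These figures assume normal data, equal arms and a common within-arm correlation.

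A reader might conclude that the planned correlations will be spurious, or that the trial's efficacy result is affected. The documents support neither. The size depends on drug effects they do not give, and neither the primary test nor the safety summaries use these correlations.

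**What to change.** - In SAP 7.3.3 and the antiviral-response correlations of 7.4.3, report the partial Spearman correlation adjusted for arm (pooled ranks centred within arm), with its P value.
- Show each arm's coefficient in Table 3.21, next to the pooled value.
- State that any claim of a link between two variables rests on the adjusted or by-arm result.
- State the baseline day for soluble mediators in 7.3.3.
- Replace the causal wording with associations in 7.3.3 and Protocol 10.2. SAP 7.4.3 already avoids it, and its comparison of ACQ-6 with the diary score over the same week can stay as it is.

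The cost is SAP wording, one option in the correlation program, some extra output and one degree of freedom. The adjusted coefficient also has lower power when drug acts on one variable through the other (86% pooled against 75% adjusted in the example), which is why the pooled value should stay alongside.

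### SAP 7.3.3 plans an open-ended set of correlations at secondary rank, worded as a search for causal relationships, with no multiplicity control and no adjustment for treatment arm

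*SAP*

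**What the plan says.** SAP 7.3.3 is headed "Correlation testing between Secondary Outcomes" and sits under 7.3, Secondary Analysis. The output index in SAP Appendix A gives it its own secondary block. The stated purpose is: "Potential causal relationships between outcome variables will be investigated using" Spearman's method. Protocol 10.2 has matching language: "rank correlations to investigate possible causal relationships".

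The list is not closed: "Tests will be carried out between (but not limited to) the following". On one side are baseline values of ACQ-6, FeNO, blood eosinophils, IgE, PC20, two skin-prick measures and the soluble mediators. On the other are peak and AUC values of lower and upper symptom scores, virus load and soluble mediators, with peak decline only for PEFR and FEV1.

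Section 7.3.3 names no significance level, test family, adjustment, key pairs, analysis set or mediator compartment. It does not say whether arms are pooled. The nearest relevant text is in SAP 7.3.1 and 7.3.2, which use P<0.05 in a hierarchy headed by the primary outcome and ask for more caution with secondary results and more still with exploratory ones.

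A second set of correlations, in SAP 7.4.3, is labelled exploratory and worded more softly: "Potential relationships between outcome variables and antiviral response variables will be investigated using" the same method.

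The Appendix B shell for Table 3.21 is titled Spearman, but its output header reads "Pearson Correlation Coefficients".

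**The concern.** About 30 subjects are to be evaluable (SAP 4.7). A large unadjusted grid in a sample of that size can be expected to produce nominally significant pairs even if nothing is related. The plan ranks this grid above the 7.4.3 correlations, which by the SAP's own scale means reading it with less caution, and it is the grid that carries the causal wording. A report that follows the plan literally could present chance findings as secondary results bearing on mechanism.

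Two features of the design could also produce correlations that say nothing about causation. Most of the clinical baselines are post-randomisation values, so the drug may already have moved them. And a mediator's baseline may be one of the values from which its own peak and AUC are calculated.

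**Working it through.** The documents give no count of tests and no expected number of false positives, so there is no planned figure to reproduce for the grid itself. The sample size behind it does reproduce: a difference of 22.21 and SD of 21.15 (SAP 4.4), two-sided 5% and 80% power, give 15 per arm by the normal approximation, hence n = 30.

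**Size of the grid**

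- Mediators: the SAP 6.3.2 list sums to 1+3+2+4+7+4+3+2+6 = 32. SAP 7.3.2 agrees: "A total of 32 mediators in nasal samples (taken at day -21, 0, 2, 3, 4, 5, 7, 10".
- Baseline side: 7 clinical variables + 32 mediators = 39.
- Outcome side: lower score 2, upper score 2, virus load 2, PEFR 1, FEV1 1, which makes 8. Adding 32 x 2 = 64 for the mediators gives 72.
- Tests: 39 x 72 = 2,808. Expected at P<0.05 if every null is true: 0.05 x 2,808 = 140.4. This expectation does not need the tests to be independent.

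| Reading of 7.3.3 | Tests | Expected at P<0.05, all nulls true |
|---|---|---|
| No mediators | 7 x 8 = 56 | 2.8 |
| Mediators as baselines only | 39 x 8 = 312 | 15.6 |
| Mediator outcomes as peak only | 39 x 40 = 1,560 | 78 |
| One compartment, peak and AUC | 39 x 72 = 2,808 | 140.4 |
| One compartment, run separately by arm | 2 x 2,808 = 5,616 | 281 |
| Nasal and bronchial (bronchial Day 5 as one outcome) | 71 x 104 = 7,384 | 369 |

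The 0.05 level is borrowed from SAP 7.3.1 and 7.3.2. Simulating the 39 x 72 grid under the complete null at n = 30 gave a mean of 142 nominal positives with independent variables (95% range 119 to 166). With an assumed correlation of 0.6 within each side, the mean was 139, the median 88 and the range 23 to 553. The realised count is therefore very uncertain. For scale, the critical |rho| at n = 30 is about 0.36 at nominal 0.05, and about 0.70 at a Bonferroni level of 0.05/2,808 = 1.8e-5.

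**Treatment arm**

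Dosing starts on Day -21. PC20 is taken on Day -9 (12 days on drug), eosinophils and IgE on Day -8 (13 days), and ACQ-6 and FeNO on Day 0 (21 days). Only the skin-prick measures come from screening. The table gives simulated false-positive rates for Spearman at 15 per arm, with arms pooled and no association within arm. The shifts are assumptions; the documents give none for these variables. The largest is the planning effect for the primary endpoint, 22.21/21.15 = 1.05 SD.

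| Drug shift, baseline / outcome (SD) | Pooled Spearman | Partial Spearman given arm |
|---|---|---|
| 0.3 / 0.3 | 5% | 5% |
| 0.5 / 0.5 | 6% | 5% |
| 0.8 / 0.8 | 11% | 5% |
| 1.05 / 1.05 | 22% | 5% |
| 0.2 / 1.05 | 6% | 5% |

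**Baseline inside its own outcome**

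SAP 4.10 sets the soluble-mediator baseline at Day 0. SAP 7.3.2 takes the nasal peak over Day 0 to Day 10, and Table 03 takes AUC over the same days. On that baseline, each of the 32 x 2 = 64 same-mediator nasal pairs is correlated by construction. As an illustration, with independent lognormal values at Days 0, 2, 3, 4, 5, 7 and 10 (an assumption), about 19% of baseline-versus-peak tests and 21% of baseline-versus-AUC tests reject. Starting the window on Day 2 returns both to about 5%. Without these pairs the one-compartment grid has 2,808 - 64 = 2,744 tests (137 expected). Bronchial samples are taken only on Day -8 and Day 5, so the overlap does not arise there.

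**The case against.** The strongest reply is that these are supportive analyses in a phase 2a trial with mechanistic aims. The text speaks only of possible or potential relationships, the SAP already asks for caution below the primary outcome, and no decision depends on the correlations. That stands as far as severity goes: the primary test's type I error is untouched. It does not supply error control. The caution clause is about differences, is not repeated in 7.3.3 and sets no rate.

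Four stronger readings are tempting and are not supported:

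- *That the trial will report about 140 false correlations.* The Appendix B shell says only what the matrix may contain, 7.3.3 restates no threshold, and 140 is an expectation under one reading with every null true. Nor is 2,808 a ceiling, since the list is open.
- *That pooling arms will seriously distort the results.* Section 7.3.3 does not say that arms are pooled, and inflation is negligible unless the drug moves both variables strongly. A pre-inoculation baseline is also a declared choice (SAP 4.10) and a reasonable one for asking whether pre-infection state predicts response. Still, SAP 7.4.1 tests for drug effects on mediators and cell counts before inoculation, so the possibility is one the plan itself recognises.
- *That Pearson coefficients will be used.* The method text, table index and shell title all say Spearman. The header is a template slip.
- *That SAP 7.4.3 has the same fault.* It also lacks an adjustment, but it is labelled exploratory, avoids causal wording, and its antiviral list is closed.

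On the overlap, 7.3.3 gives no day for the mediator baseline, and SAP 7.3.2 uses Day -21 for nasal change scores. The 64 pairs are affected if the SAP 4.10 definition applies.

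**Conclusion.** The concern holds as one of labelling, definition and error control. SAP 7.3.3 puts an unbounded family of correlations at secondary rank, gives it a causal purpose and sets no error rate. Run in full with one mediator compartment, it implies 2,808 tests and about 140 nominal positives if every null is true at 0.05; the readings span 56 tests (2.8) to 7,384 (369). Missing arm adjustment is a secondary weakness: at n = 30 the pooled false-positive rate stays near 5 to 6% for shifts up to 0.5 SD in both variables and reaches 22% only at 1.05 SD in both. The built-in overlap affects 64 nasal pairs under a Day 0 baseline. This should be changed, but it does not threaten the primary analysis.

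**What to change.** - Move SAP 7.3.3 under 7.4 as exploratory.
- In SAP 7.3.3 and Protocol 10.2, replace the causal wording with associations (hypothesis-generating).
- Close the list, and state the mediator compartment and the analysis set (FAS).
- Report partial Spearman correlations adjusted for treatment arm, with Benjamini-Hochberg adjusted P values within each defined block: clinical by clinical, mediator with clinical, and mediator by mediator.
- State the mediator baseline day. If it is Day 0, drop the same-mediator pairs or start their peak and AUC after Day 0.
- Change the Table 3.21 shell header from Pearson to Spearman.

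The cost is document wording and a few lines of code, with no new data. The small downside is that fewer correlations will be called significant.
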